## 7.5 Sponsor Responsibility for Reporting Adverse Events

All Adverse Events will be reported to regulatory authorities, IRB/IECs and investigators in accordance with all applicable global laws and regulations.

## 8 Statistical Analysis Plan

### 8.1 Statistical Analysis Plan Summary

This is a non-randomized prospective Phase II clinical trial with a Simon stage II design with an early stopping provision. The primary objective is to evaluate the overall response rate (ORR) by week 12 in patients with stage III unresectable/stage IV melanoma. The hypothesis is that the study treatment regimen will have a clinical meaningful improvement in ORR by week 12. H0 is for an ORR by week 12 = 60% while Ha is for an ORR by week 12= 80%. 60% is used as a threshold for the H0 based on published data (19).

### 8.2 Sample Size and Accrual Rate Considerations

#### 8.2.1 Sample Size and Power Estimate

A two-stage Simon's optimal design is used for the study to test the null hypothesis that the ORR by week 12 is 60% or less versus the alternative hypothesis that the ORR by week 12 is greater than 80% using an one-sided test with 5% level of significance with the power of 80% for alternative hypothesis. An initial 11 evaluable patients will be accrued at the end of stage 1. If at least 4 or more overall responders (CR/PR per RECIST 1.1) from stage 1 are observed, the study will continue to enroll additional 32 evaluable patients in the stage 2. The null hypothesis will be rejected at the 5% level of significance (one-sided) if there are 30 or fewer ORR by week 12 among all 43 evaluable patients by the end of stage 2. If the ORR rate is 60%, the probability of ending the study during the first stage is 70%; if the ORR rate is indeed 80%, the probability of study will be terminated at the first stage is 16%. The significance level of the study is 0.05 and the power is 0.80 for the study design.

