## 3 Study Design

### 3.1 Characteristics

This is a single arm, single institution, open label, prospective, Phase II clinical trial with a Simon stage II design with an early stopping rule. In the first stage 11 patients will be accrued. If  $\leq 7$  responses are seen here then the trial will be stopped for futility. If  $>7$  responses are seen then the trial will be continued and a full 43 patients will be enrolled.

Patients will take aspirin daily and receive combination therapy with pembrolizumab and ipilimumab every 3 weeks for 4 cycles. After 4 cycles, ipilimumab will be discontinued and patients will receive pembrolizumab every 3 weeks and continue taking aspirin daily.

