### 8.3 Interim Analyses and Stopping Rules

The two stage sequential design of this study has a decision timepoint based on the counts of CR or PR (per RECIST 1.1) from stage 1 by at least 4 months post-initial treatment regimen of the 11 patients with measurable disease at baseline, to either stop or initiate stage 2 of the study. In the first stage 11 patients will be accrued. If  $\leq 7$  responses are seen here then the trial will be stopped

for futility. If >7 responses are seen then the trial will be continued an a full 43 patients will be enrolled.

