## 8.4 Statistical Analysis Plan

This is a Simon 2 stage Phase II prospective clinical trial. The statistical plan will be for an optimal 2 stage design with the  $P_0=0.6$  and  $P_1=0.8$ . If <30 responses are seen then the experimental hypothesis has been rejected. The type 1 error is 0.0489 and the power is 0.8024. The probability of early stopping if the response rate is  $P_0=20.5\%$

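### The stage 1 futility rule is written two incompatible ways (continue with 4 or more of 11; stop with 7 or fewer), and early stopping under the null is given as both 70% and 20.5%

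*Combined protocol and SAP*

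**What the plan says.** The design is named in section 8.2.1: "A two-stage Simon's optimal design is used for the study". The hypotheses are in section 8.1: "H0 is for an ORR by week 12 = 60% while Ha is for an ORR by week 12= 80" per cent. Section 8.2.1 sets the error rates, "using an one-sided test with 5% level of significance with the power of 80% for alternative hypothesis", with 11 evaluable patients in stage 1 and 32 more in stage 2, 43 in all.

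The stage 1 decision appears three times:

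- Section 8.2.1: "If at least 4 or more overall responders (CR/PR per RECIST 1.1) from stage 1 are observed, the study will continue". This means stopping at 3 or fewer.
- Section 8.3: "If >7 responses are seen then the trial will be continued an a full 43 patients will be enrolled". The sentence before it stops the trial for futility at 7 or fewer.
- Section 3.1 gives the same threshold as 8.3: with more than 7, "responses are seen then the trial will be continued and a full 43 patients will be enrolled".

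The probability of stopping early under the null appears twice:

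- Section 8.2.1: "If the ORR rate is 60%, the probability of ending the study during the first stage is 70" per cent. The same sentence gives 16% if the response rate is 80%.
- Section 8.4: the sentence that begins "The probability of early stopping if the response rate is" ends with P0 set equal to 20.5%, although the same section has just defined P0 as 0.6.

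Section 8.4 also states a type I error of 0.0489 and a power of 0.8024.

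**The concern.** The three statements govern one decision on one group of 11 patients. At 3 or fewer responses they all stop, and at 8 or more they all continue. At 4 to 7, section 8.2.1 opens stage 2 while sections 3.1 and 8.3 close the trial. Nothing in the documents says which section prevails.

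This is the trial's only formal futility look, and it decides whether 32 more patients receive the triple combination. The trial is open label with a single arm, so if the interim count falls between 4 and 7, the choice between two written rules would be made with the responses already known. If 8.2.1 were followed, there would be almost no futility stop, and the stated error rates would no longer describe the trial.

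The second figure, 20.5%, removes the easiest way to settle the matter. A reader who tries to identify the intended rule from its early-stopping probability finds two values in the plan.

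**Working it through.** **Inputs.** p0 = 0.60 and p1 = 0.80 (8.1, 8.4); n1 = 11, n2 = 32, n = 43 (8.2.1); stage 1 stopping bound r1 = 7 (3.1, 8.3) or r1 = 3 (8.2.1); final bound r = 30 (8.2.1, 8.4), taken as success with 31 or more of 43.

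**Formulas.** With X1 ~ Bin(11, p) and X2 ~ Bin(32, p):

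- early stopping: PET(p) = P(X1 ≤ r1)
- probability of declaring success: sum over x1 > r1 of P(X1 = x1) × P(X2 ≥ 31 − x1)
- expected sample size: 11 + (1 − PET) × 32

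**Early stopping**

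| Stage 1 rule | p = 0.60 | p = 0.80 |
|---|---|---|
| Stop at ≤7 | 0.7037 | 0.1611 |
| Stop at ≤3 (continue at ≥4) | 0.0293 | 0.0002 |

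The first row is the plan's 70% and 16%. The second row is neither.

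**Probability of success, by stage 1 count**

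| x1 | X2 needed | p = 0.60: P(x1) × tail | p = 0.80: P(x1) × tail |
|---|---|---|---|
| 11 | ≥20 | 0.0036 × 0.4618 = 0.0017 | 0.0859 × 0.9939 = 0.0854 |
| 10 | ≥21 | 0.0266 × 0.3233 = 0.0086 | 0.2362 × 0.9833 = 0.2323 |
| 9 | ≥22 | 0.0887 × 0.2046 = 0.0181 | 0.2953 × 0.9589 = 0.2831 |
| 8 | ≥23 | 0.1774 × 0.1156 = 0.0205 | 0.2215 × 0.9102 = 0.2016 |
| **Sum, 8 to 11** | | **0.0489** | **0.8024** |
| 7 | ≥24 | 0.2365 × 0.0575 = 0.0136 | 0.1107 × 0.8254 = 0.0914 |
| 6 | ≥25 | 0.2207 × 0.0248 = 0.0055 | 0.0388 × 0.6982 = 0.0271 |
| 5 | ≥26 | 0.1471 × 0.0091 = 0.0013 | 0.0097 × 0.5355 = 0.0052 |
| 4 | ≥27 | 0.0701 × 0.0028 = 0.0002 | 0.0017 × 0.3602 = 0.0006 |
| **Sum, 4 to 11** | | **0.0695** | **0.9266** |

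(Products and sums were computed unrounded, so the last digit can differ from the rounded entries.)

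Stopping at 7 or fewer reproduces the stated type I error of 0.0489 and power of 0.8024 to four decimals. Continuing at 4 or more gives 0.0695 and 0.9266.

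**Check on the design name.** A search over two-stage designs with total size 30 to 55, type I error at most 0.05 and power at least 0.80 finds the smallest expected sample size under p0 at exactly 7/11 and 30/43. This is the optimal design that section 8.2.1 names.

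**The disputed range.** P(4 ≤ X1 ≤ 7) is 0.7037 − 0.0293 = 0.674 at p = 0.60, and 0.1611 − 0.0002 = 0.161 at p = 0.80.

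**The 20.5% figure.** At p = 0.60, P(X1 ≤ 4) = 0.0994 and P(X1 ≤ 5) = 0.2465, so no cut-off among 11 patients gives 0.205. The expected sample size under p0 does match the number:

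- stop at ≤7: 11 + (1 − 0.7037) × 32 = 20.48 patients
- stop at ≤3: 11 + (1 − 0.0293) × 32 = 42.06 patients

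**The case against.** The strongest reply is that the intended rule is not really in doubt. The section devoted to interim analyses and the study design section agree on 7 or fewer, and all four stated operating characteristics fit that rule alone. The clause in 8.2.1 is therefore most plausibly a drafting slip, and a team working from 8.3 would stop correctly. This stands as an account of intent. It also means that 0.674 is the probability of reaching the disputed range at a 60% response rate, not the probability of a wrong decision. But the outlying rule sits in the sample-size section, where a statistician or monitoring committee would look for it, and the text gives no order of precedence.

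Two further points are fair:

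- No section states an expected sample size, so reading 20.5 as that quantity mislabelled is an inference from the numerical match. The sentence in 8.4 is also garbled. That 20.5% is wrong as a stopping probability does not depend on the inference.
- The value 0.0695 assumes success at 31 or more of 43. Section 8.2.1 instead rejects the null at 30 or fewer, the wrong direction for an efficacy test, and 8.4 writes fewer than 30 as failure, which leaves exactly 30 undecided. Counting 30 as a success would give a type I error of 0.0794 even when stopping at 7 or fewer. This is a separate defect and does not weaken the point about stage 1.

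**Conclusion.** The concern holds. The current text contains two stage 1 rules that conflict at 4, 5, 6 and 7 responses, and two early-stopping probabilities under the null, of which only the 70% (exactly 70.4%) is right.

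The plan's own figures identify the rule that stops at 7 or fewer as the one the design was built on. Following 8.2.1 as written would cut early stopping under the null from 70.4% to 2.9%, raise expected sample size under the null from 20.5 to 42.1 patients, and put the type I error at 0.0695 against a one-sided limit of 5%. Power would rise from 0.802 to 0.927, so the change would trade away the futility protection and the error control.

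These results are exact binomial calculations at response rates of 60% and 80%, with all 43 patients evaluable and success at 31 or more. The plan must be corrected before the interim decision.

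**What to change.** 1. In section 8.2.1, replace the threshold of 4 responders with at least 8 (more than 7) of 11, to match sections 3.1 and 8.3.
2. In section 8.4, replace the 20.5% statement with: the probability of early stopping under P0 = 0.6 is 70.4%, and the expected sample size under P0 is 20.5 patients.
3. In the same amendment, reconcile the final decision rule in 8.2.1 and 8.4. The stated type I error and power require rejecting the null with 31 or more of 43 and not rejecting it with 30 or fewer.

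Items 1 and 2 change two figures. The amendment needs protocol review committee and IRB approval before implementation (section 9.4). No patients are added, and the design and its stated operating characteristics stay as they are.

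### The final decision rule in Section 8.2.1 is reversed and Section 8.4 mishandles exactly 30 responders; the stated type I error of 0.0489 requires 31 or more of 43

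*Combined protocol and SAP*

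**What the plan says.** Section 8.1 sets the hypotheses: "H0 is for an ORR by week 12 = 60% while Ha is for an ORR by week 12= 80" (per cent). Section 8.2.1 specifies a Simon optimal two-stage design, one-sided 5% level, 80% power, with 11 evaluable patients in stage 1 and 32 more in stage 2, 43 in all.

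The plan then gives these rules and figures:

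- **Final rule, Section 8.2.1:** "The null hypothesis will be rejected at the 5% level of significance (one-sided) if there are 30 or fewer ORR by week 12", out of 43.
- **Final rule, Section 8.4:** "If <30 responses are seen then the experimental hypothesis has been rejected". Nothing is said about exactly 30.
- **Stage 1 rule, Section 8.2.1:** "If at least 4 or more overall responders (CR/PR per RECIST 1.1) from stage 1 are observed, the study will continue".
- **Stage 1 rule, Section 8.3 (same rule in Section 3.1):** "If >7 responses are seen then the trial will be continued an a full 43 patients will be enrolled"; with 7 or fewer the trial stops for futility.
- **Operating characteristics, Section 8.4:** "The type 1 error is 0.0489 and the power is 0.8024".
- **Early stopping, Section 8.2.1:** "If the ORR rate is 60%, the probability of ending the study during the first stage is 70" (per cent), and 16% if the true rate is 80%.
- **Early stopping, Section 8.4:** "The probability of early stopping if the response rate is" P0 is given as 20.5%.

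**The concern.** A one-sided test of 60% or less against a higher rate cannot reject on a low count, so the sentence in Section 8.2.1 contradicts the hypotheses in the same paragraph. A reader will see that the direction is a slip. The less visible problem is which side the count of 30 falls on.

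Turning the Section 8.2.1 sentence round to 30 or more would match the complement of the Section 8.4 rule, and so would look confirmed. It would also exceed the stated 5% level. If the trial ended on exactly 30 of 43, the primary conclusion would be settled after the data were known.

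The surrounding text is not a safe guide. With 4 to 7 responders in stage 1, Section 8.2.1 tells the team to enrol 32 more patients, and Sections 3.1 and 8.3 tell it to stop.

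**Working it through.** **Inputs.** p0 = 0.60 and p1 = 0.80 (Section 8.1); n1 = 11, n2 = 32, n = 43 (Section 8.2.1); stage 1 rule of more than 7 of 11 (Sections 3.1 and 8.3) or at least 4 of 11 (Section 8.2.1).

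**Formula.** With X1 ~ Bin(11, p) and X2 ~ Bin(32, p) independent, continuing if X1 > r1 and rejecting if X1 + X2 ≥ R:

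P(reject) = Σ over x > r1 of P(X1 = x) · P(X2 ≥ R − x).

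**Step 1: reproduce the plan's figures.** Take r1 = 7 and R = 31.

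| x | P(X1 = x), p = 0.6 | P(X2 ≥ 31 − x), p = 0.6 | Product | P(X1 = x), p = 0.8 | P(X2 ≥ 31 − x), p = 0.8 | Product |
|---|---|---|---|---|---|---|
| 8 | 0.17737 | 0.11555 | 0.02050 | 0.22146 | 0.91017 | 0.20157 |
| 9 | 0.08868 | 0.20459 | 0.01814 | 0.29528 | 0.95891 | 0.28315 |
| 10 | 0.02661 | 0.32330 | 0.00860 | 0.23622 | 0.98328 | 0.23227 |
| 11 | 0.00363 | 0.46181 | 0.00168 | 0.08590 | 0.99395 | 0.08538 |
| Sum | | | **0.0489** | | | **0.8024** |

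Both stated figures reproduce to four decimals. Early stopping, P(X1 ≤ 7), is 0.7037 at 60% and 0.1611 at 80%, matching the 70% and 16% in Section 8.2.1.

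**Step 2: uniqueness.** A scan of every stage 1 cut-off with every final boundary from 21 to 43, at n1 = 11 and n = 43, returns 0.0489 and 0.8024 for this pair only. A search for the optimal design (type I error at most 0.05, power at least 0.80, n up to 55) also gives 7/11 and 30/43, where 30 is the largest count that does *not* reject.

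**Step 3: the alternatives.**

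| Continue if | Reject if | P(reject) at 60% | P(reject) at 80% |
|---|---|---|---|
| > 7 of 11 | ≥ 31 of 43 | 0.0489 | 0.8024 |
| > 7 of 11 | ≥ 30 of 43 | 0.0794 | 0.8232 |
| > 7 of 11 | ≤ 30 of 43 (Section 8.2.1 literally) | 0.2474 | 0.0365 |
| ≥ 4 of 11 | ≥ 31 of 43 | 0.0695 | 0.9266 |
| ≥ 4 of 11 | ≥ 30 of 43 | 0.1237 | 0.9637 |

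The literal row is P(continue) minus P(reject at ≥ 31): 0.2963 − 0.0489 = 0.2474 and 0.8389 − 0.8024 = 0.0365.

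**Step 4: how often 30 would matter.** P(continue and exactly 30) is 0.0794 − 0.0489 = 0.0305 at 60% and 0.8232 − 0.8024 = 0.0209 at 80% (each from unrounded values). Among trials that reach stage 2, that is 0.0305/0.2963 = 10.3% and 0.0209/0.8389 = 2.5%.

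**Step 5: the stage 1 conflict.** With at least 4 of 11, early stopping is P(X1 ≤ 3) = 0.0293 at 60% and 0.0002 at 80%. Expected sample size at 60% is 11 + (1 − 0.0293) × 32 = 42.06, against 11 + 0.2963 × 32 = 20.48 with more than 7. The two rules give opposite instructions when X1 is 4 to 7, which has probability 0.7037 − 0.0293 = 0.6744 at 60% and 0.1611 − 0.0002 = 0.1609 at 80%.

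**Step 6: the 20.5%.** P(X1 ≤ k) at 60% is 0.0994, 0.2465, 0.4672 and 0.7037 for k = 4, 5, 6 and 7. No cut-off out of 11 gives 0.205. The expected sample size under the null hypothesis, 20.48 patients, is a plausible source of the figure, though the documents do not confirm it.

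**The case against.** The best defence is that 0.0794 is not a property of the plan as written, because no section says 30 or more. One could equally repair Section 8.2.1 by inserting the word *not* before *be rejected*. That places 30 with the failures and gives exactly 31 or more and 0.0489. On this view the cut between 30 and 31 is already in print, and the stated 5% level rules out the other reading without a full recomputation.

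The practical reach is also limited. Ending on exactly 30 has a probability of about 3% at a 60% rate and 2% at 80%. Section 8.4.1 reports the primary endpoint as an estimate with a 95% interval. The exact intervals for 30/43 (53.9% to 82.8%) and 31/43 (56.3% to 84.7%) are close, and both include 60%.

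Much of this stands. The 0.0794 is conditional on one particular repair, the chance of landing on 30 is small, and the stage 1 conflict affects more possible outcomes than the final boundary does. But two repairs of Section 8.2.1 are available, and the complement of the Section 8.4 rule points to the wrong one. Section 8.4.1 offers no other success criterion, so the formal test in Sections 8.2.1 and 8.4 remains the decision rule, and it should not depend on the reader re-deriving it.

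**Conclusion.** The point holds. The primary decision rule in Section 8.2.1 contradicts its own hypotheses, and Section 8.4 does not put 30 responders on the correct side. The plan's stated error rates identify the intended design: continue with more than 7 of 11, reject with 31 or more of 43. Treating 30 as a success raises the one-sided type I error from 0.0489 to 0.0794 and power from 0.8024 to 0.8232. Correcting the final boundary but keeping the 4-of-11 rule still gives 0.0695 and cuts early stopping under the null hypothesis from 70.4% to 2.9%.

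These figures assume independent responses with a common rate and exactly 11 and 43 evaluable patients; the 0.0794 also assumes the rule of more than 7 of 11. The design and sample size need no change. The correction is nevertheless necessary, because the sentences at fault decide whether the trial continues and whether it succeeds.

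**What to change.** Make four sentence edits in one protocol amendment:

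1. **Section 8.2.1, final rule:** *H0 will be rejected if 31 or more responders are observed among the 43 evaluable patients; with 30 or fewer, H0 is not rejected.*
2. **Section 8.4, final rule:** change the failure condition from fewer than 30 responses to 30 or fewer.
3. **Section 8.2.1, stage 1 rule:** replace the 4-responder threshold so that it agrees with Sections 3.1 and 8.3 (continue only with more than 7 of 11).
4. **Section 8.4, early stopping under P0:** replace 20.5% with 70.4%. If the sponsor confirms that 20.5 was meant as the expected sample size under the null hypothesis, report it as that, in patients.

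Edits 1 to 3 together make the rules agree with the stated 0.0489 and 0.8024. Edit 3 alone makes them agree with the stated 70% and 16%. Edit 4 removes the remaining conflict between Sections 8.2.1 and 8.4. The cost is the amendment itself, with no added patients, visits or procedures.

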#### 8.2.2 Replacement Policy

Patients who are of unknown clinical response and discontinued due to AEs will be treated as non-responders. Other missing data will simply be noted as missing on the appropriate table or listing. Patients with missing data will not be replaced.

#### 8.2.3 Accrual Estimates

The study is planned to accrue a total of 43 evaluable patients. The accrual rate is expected to be approximately 2 to 3 patients per month. It is expected to take about 24 months to accrue all 43 evaluable patients. We expect to enroll up to 50 patients to offset the potential drop-outs or non-evaluable patients in the study.

### 8.3 Interim Analyses and Stopping Rules

The two stage sequential design of this study has a decision timepoint based on the counts of CR or PR (per RECIST 1.1) from stage 1 by at least 4 months post-initial treatment regimen of the 11 patients with measurable disease at baseline, to either stop or initiate stage 2 of the study. In the first stage 11 patients will be accrued. If  $\leq 7$  responses are seen here then the trial will be stopped

for futility. If >7 responses are seen then the trial will be continued an a full 43 patients will be enrolled.

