The combination of ipilimumab and pembrolizumab is considered one of the most effective regimens currently in use (Long et al, ASCO 2016) with an ORR of >50% with reduced grade 3/4 toxicities compared to the combination of ipilimumab and nivolumab. Given that this current combination is adding a drug (ASA), ipilimumab pembrolizumab is a better choice for the baseline regimen

The addition of ASA is based on preclinical data showing the effectiveness of ASA in increasing responses to anti-PD-1 antibodies(3)In this study mice were administered aspirin orally at 600  $\mu$ g/mL. translating this dose to a human dose, approximately 1,800-2,400 mg/day would be appropriate. In a twice daily dose this would be 975 mg (total 1,950 mg/day).

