### **5.3.1 Dose Modification for Pembrolizumab**

Adverse events (both non-serious and serious) associated with pembrolizumab exposure may represent an immunologic etiology. These adverse events may occur shortly after the first dose or several months after the last dose of treatment. Pembrolizumab must be withheld for drug-related toxicities and severe or life-threatening AEs as per 3 below. See Section 5.6 for supportive care guidelines, including use of corticosteroids.

**Table 2 Pembrolizumab Dose Modification and Toxicity Management Guidelines for Immune-related AEs Associated with Pembrolizumab**

General instructions: 
 
1. Corticosteroid taper should be initiated upon AE improving to Grade 1 or less and continue to taper over at least 4 weeks.
 
2. For severe and life-threatening irAEs, IV corticosteroid should be initiated first followed by oral steroid. Other immunosuppressive treatment should be initiated if irAEs cannot be controlled by corticosteroids.
 
				
Immune-related AEs	Toxicity grade or conditions (CTCAEv4.0)	Action taken to pembrolizumab	irAE management with corticosteroid and/or other therapies	Monitor and follow-up
Pneumonitis	Grade 2	Withhold	
 
• Administer corticosteroids (initial dose of 1-2 mg/kg prednisone or equivalent) followed by taper
 
	
 
• Monitor participants for signs and symptoms of pneumonitis
 
• Evaluate participants with suspected pneumonitis with radiographic imaging and initiate corticosteroid treatment
 
• Add prophylactic antibiotics for opportunistic infections
 

	Grade 3 or 4, or recurrent Grade 2	Permanently discontinue		

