**Table 3 Ipilimumab Dose Modification Guidelines for Drug-Related Adverse Events**

Toxicity	Hold For Grade	Timing for Restarting Treatment	Treatment Discontinuation
Diarrhea/Colitis	2	Toxicity resolves to Grade 0-1	Toxicity does not resolve within 12 weeks of last dose or inability to reduce corticosteroid to 10 mg or less of prednisone or equivalent per day within 12 weeks. Patients are to be treated with 1 mg/kg prednisone or equivalent if grade 2 or greater toxicity and tapered over several weeks
	3-4	Permanently discontinue	Permanently discontinue
AST, ALT, or Increased Bilirubin	2	Toxicity resolves to Grade 0-1	Toxicity does not resolve within 12 weeks of last dose
	3-4	Permanently discontinue (see exception below) a	Permanently discontinue
Type 1 diabetes mellitus (if new onset) or Hyperglycemia	T1DM or 3-4	Hold ipilimumab for new onset Type 1 diabetes mellitus or Grade 3-4 hyperglycemia associated with evidence of beta cell failure	Discontinue permanently
Hypophysitis	2-4	Toxicity resolves to Grade 0-1. Therapy with pembrolizumab can be continued while endocrine replacement therapy is instituted	Toxicity does not resolve within 12 weeks of last dose or inability to reduce corticosteroid to 10 mg or less of prednisone or equivalent per day within 12 weeks
Hyperthyroidism	3	Toxicity resolves to Grade 0-1	Toxicity does not resolve within 12 weeks of last dose or inability to reduce corticosteroid to 10 mg or less of prednisone or equivalent per day within 12 weeks
	4	Permanently discontinue	Permanently discontinue
Hypothyroidism		Therapy with ipilimumab can be continued while thyroid replacement therapy is instituted	Therapy with ipilimumab can be continued while thyroid replacement therapy is instituted
Infusion Reaction	2 b	Toxicity resolves to Grade 0-1	Permanently discontinue if toxicity develops despite adequate premedication
	3-4	Permanently discontinue	Permanently discontinue
Pneumonitis	2	Toxicity resolves to Grade 0-1	Toxicity does not resolve within 12 weeks of last dose or inability to reduce corticosteroid to 10 mg or less of prednisone or equivalent per day within 12 weeks
	3-4	Permanently discontinue	Permanently discontinue
Renal Failure or Nephritis	2	Toxicity resolves to Grade 0-1	Toxicity does not resolve within 12 weeks of last dose or inability to reduce corticosteroid to 10 mg or less of prednisone or equivalent per day within 12 weeks
	3-4	Permanently discontinue	Permanently discontinue

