**Table 4 Aspirin Dose Modification Guidelines for Drug-Related Adverse Events**

Toxicity	Hold Treatment For Grade	Timing for Restarting Treatment	Treatment Discontinuation
GI Bleeding	2	Toxicity resolves to Grade 0-1	Toxicity does not resolve within 2 weeks, or continued bleeding, or life threatening or serious Grade 3 or 4 hemorrhage
	3-4	Permanently discontinue	Permanently discontinue
Renal Failure or Nephritis	2	Toxicity resolves to Grade 0-1	Toxicity does not resolve within 4 weeks
GI Ulceration	1-2	Use omeprazole or PPI or sucralfate if not currently being used	May continue aspirin if symptoms resolve with treatment
	3-4 or Severe	Toxicity resolves to Grade 1 or 0	Life threatening or serious Grade 3 or 4 toxicity

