#### **7.3.3 Protocol-Specific Exceptions to Serious Adverse Event Reporting**

Efficacy endpoints as outlined in this section will not be reported to Merck as described in Section 7.3 - Immediate Reporting of Adverse Events to the Sponsor and to Merck, unless there is evidence suggesting a causal relationship between the drug and the event. Any such event will be submitted to the Sponsor within 24 hours and to Merck Global Safety within 2 working days either by electronic or paper media.

Specifically, the suspected/actual events covered in this exception include any event that is disease progression of the cancer under study.

The Sponsor will monitor unblinded aggregated efficacy endpoint events and safety data to ensure the safety of the subjects in the trial. Any suspected endpoint which upon review is not progression of the cancer under study will be forwarded to Merck Global Safety as a SAE within 2 working days of determination that the event is not progression of the cancer under study. Hospitalization related to convenience (e.g. transportation issues etc.) will not be considered a SAE.

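### Stage 2 opens on response counts alone: adding a recorded safety go decision and a default enrolment pause after a treatment-related death would be a cheap safety improvement

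*Combined protocol and SAP*

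**What the plan says.** **The stage decision.** Section 8.3 states: "The two stage sequential design of this study has a decision timepoint based on the counts of CR or PR", taken at least 4 months after the 11 stage-1 patients start treatment. Section 3.1 says that if more than 7 "responses are seen then the trial will be continued and a full 43 patients will be enrolled". Section 8.2.1 says that if 4 or more responders "from stage 1 are observed, the study will continue to enroll additional 32 evaluable patients in the stage 2". The two thresholds conflict, but neither rule has a safety element.

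**Safety oversight.** There is a good deal of it.
- Appendix 3 (Monitoring and Reporting Guidelines; 3.1) has the Site Committee review participant safety and Grade 3-5 events every month and record the discussion in minutes.
- Appendix 3, 3.2 has the DSMC review serious adverse events continuously and meet every six weeks.
- Section 7.3.3: "The Sponsor will monitor unblinded aggregated efficacy endpoint events and safety data to ensure the safety of the subjects in the trial".
- Each drug has patient-level rules. Section 5.3.1 says "Pembrolizumab must be withheld for drug-related toxicities and severe or life-threatening AEs"; Table 3 gives "Ipilimumab Dose Modification Guidelines for Drug-Related Adverse Events" and Table 4 "Aspirin Dose Modification Guidelines for Drug-Related Adverse Events".
- Section 5.6.7 makes a potential health hazard a ground for ending the trial early.

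**Actions at trial level.** Under Appendix 3, a death at least possibly related to treatment must be reported to the DSMC Chair or Vice Chair and to its Director within one business day. A Grade 3-4 rate above that in the Investigator Brochure or package insert leads to a report to the DSMC. An enrolment hold is mentioned only as a voluntary act of the investigator.

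**The concern.** Section 1.4 says "The addition of ASA is based on preclinical data", and the documents cite no human safety data for the three drugs given together. Stage 1 is therefore the first safety experience with the triplet that the documents provide for, and its end is the natural point to ask whether toxicity is acceptable. The plan asks only whether enough patients responded.

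A patient with a confirmed response and severe toxicity still counts towards opening stage 2. Section 8.2.2 counts a patient who stopped for adverse events as a non-responder only if the response is unknown.

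At stake are the 32 patients who enter after the look. Separately, enrolment may continue after a related death unless someone chooses to hold it.

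**Working it through.** **1. The plan's own figures.** Inputs: p0 = 0.60 and p1 = 0.80 (8.1), 11 then 32 patients (8.2.1), stop at 7 or fewer of 11 (8.3). With X ~ Bin(11, p) and Y ~ Bin(32, p):
- P(early stop) = P(X ≤ 7) = 0.7037 at p = 0.60 and 0.1611 at p = 0.80, matching the 70% and 16% in 8.2.1.
- P(reject H0) = sum over x = 8 to 11 of P(X = x) × P(Y ≥ 31 − x) = 0.0489 at 0.60 and 0.8024 at 0.80, matching 8.4.

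The response rule with more than 7 of 11 therefore reproduces. With continuation at 4 or more of 11, as 8.2.1 words it, early stopping at p = 0.60 falls to 0.029 and type I error rises to 0.0695.

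**2. How much review precedes the look.** Accrual is 2 to 3 patients a month (8.2.3). Six weeks is 1.38 months. Assume the look comes 4 months after the last stage-1 patient starts.
- Look at 11/3 + 4 = 7.67 to 11/2 + 4 = 9.5 months.
- DSMC cycles by then: 7.67/1.38 = 5.6 to 9.5/1.38 = 6.9.
- DSMC cycles within the 4-month wait: 4/1.38 = 2.9, so 2 to 3 scheduled meetings.

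What is missing is a decision tied to stage 2, not scrutiny.

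**3. Exposure after the look.** Stage 2 adds 43 − 11 = 32 patients, or up to 50 − 11 = 39 if the whole drop-out allowance in 8.2.3 enters then. Section 1.2.2 gives about 20% Grade 3/4 events for the backbone without aspirin. At assumed triplet rates of 30%, 40% and 50%, the excess among 32 is 32 × 0.10 = 3.2, 32 × 0.20 = 6.4 and 32 × 0.30 = 9.6. These counts illustrate exposure only.

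**4. What 11 patients can show.** P(at least one event) = 1 − (1 − r)^11 = 0.43 at r = 5%, 0.69 at 10% and 0.91 at 20%. A binding count is a poor tool here. Stopping at 5 or more Grade 3/4 patients of 11 would detect a true 40% rate with probability 0.47 and a 50% rate with 0.73. If toxicity is independent of response, it would also cut power to about 0.8024 × 0.950 = 0.76 at a true rate of 20%. The go decision should therefore be a judgement.

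**5. Cost of the two additions.**
- Go decision not timed to the look: at most one cycle, 1.38 × 2 to 1.38 × 3 = 2.8 to 4.1 entries; on average half of that, 1.4 to 2.1.
- Death pause, at an assumed related-death rate of 1% to 2%: P(at least one death in 43) = 1 − (1 − r)^43 = 0.35 to 0.58. Expected pauses are 43r = 0.43 to 0.86. At a full cycle each, that is 0.59 to 1.19 months, or 1.2 (0.59 × 2) to 3.6 (1.19 × 3) delayed entries in total. This is an upper bound, because a Chair decision is quicker and a death after the last entry pauses nothing.

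**The case against.** The strongest reply is that safety is already closely followed. Dated Site Committee minutes will exist many times over before the look, and the DSMC reviews serious events between its six-weekly meetings. The health-hazard criterion in 5.6.7 has no timing, so it applies throughout, including when stage 2 opens. The DSMC leadership hears of a related death within one business day, and the investigator can hold enrolment at once. All of this stands. It rules out reading the plan as one in which nobody watches safety.

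Three further inferences are tempting, and the documents do not support them.
- *The Simon design is faulty.* With more than 7 of 11 it reproduces, and a response-only futility rule is normal.
- *The fix would prevent 3 to 10 severe events.* The rates are assumed and no trigger is proposed, so nothing shows how many events a sign-off would avert.
- *Three or four patients will start after a death before anyone acts.* That requires the Chair, the Director, the investigator and the sponsor all to do nothing for a whole cycle.

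It can also be said that the rule may sit in the NCI-approved monitoring plan named in 9.7, which was not available, or in the text after Appendix 3's section on adverse event rates, which was removed before review. That is possible, and it limits the point to the text supplied.

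What survives is narrow. The minutes record discussion but do not control stage 2, 5.6.7 names no decision-maker, and the two reporting duties in Appendix 3 require no pause.

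**Conclusion.** The point holds as a cheap safety improvement, not as an error. In the supplied text stage 2 opens on response counts alone, and a related death requires a report but no pause. Two things are missing: a safety go/no-go tied to opening stage 2 for 32 further patients, and a default pause after a related death.

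Confidence is medium, because the governing monitoring plan was not available. The benefit cannot be put in numbers from these documents. The cost can be bounded, and it is small. It rests on 2 to 3 entries a month, six-weekly DSMC meetings and, for the total across pauses, the assumed 1% to 2% related-death rate.

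**What to change.** 1. In 3.1, 8.2.1 and 8.3 add:
> Stage 2 opens only when the response rule in 8.3 (more than 7 of 11) is met and the DSMC has recorded a go decision after reviewing related Grade 3-5 events in all stage-1 patients.

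Time the review to the response look at 4 months or later, and correct the conflicting threshold of 4 in 8.2.1 in the same amendment.

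2. In Appendix 3, 3.2 add:
> A death judged possibly, probably or definitely related to study treatment pauses new enrolment until the DSMC, or its Chair or Vice Chair on an expedited basis, records a decision.

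If the NCI-approved monitoring plan already contains either rule, cite it in 8.3 and Appendix 3 instead.

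**Cost.** An amendment needs PRC and IRB approval (9.4), and the DSMC must accept a go/no-go role that the supplied text does not expressly give it. No new data are collected. The go decision adds close to no delay if timed to the look. Each related death costs at most one six-week cycle, about 3 to 4 entries, and less with a Chair decision. No numeric trigger is added, so the response rule's type I error and power stay as stated unless the DSMC stops for safety. Such a stop can only lower type I error, at some cost in power.
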